### **Secondary:**

1- Disease control rate (DCR). Defined by absence of radiological progression in conventional imaging examinations by RECIST 1.1 at 3 months after the end of treatment. For patients with functioning syndrome, beside radiological DCR, patients should have improved in at least 10% of the baseline score of quality-of-life (EORTC QLQ-GINET21) and stability or decrease in tumor markers.

2- Progression-free survival. Defined by time from day 1 cycle 1 to death from any cause or radiological progression by RECIST 1.1, whichever occurs first. Patients alive and without progression at the time of study analysis will be censored for time-to-event analysis.

3- Radiological response rate. Assessed by RECIST 1.1 criteria.

4- Rate of Biochemical response. Defined by at least 30 percent drop in the tumor marker (24-hour urine 5-hydroxyindoleacetic acid (5-HIAA) and/or specific hormone), if functioning syndrome, at any time of treatment in relation to pre-treatment value.

5- Quality of life. Assessed by the EORTC QLQ-C30 and QLQ-GINET21; both available in Brazilian Portuguese. Improvement of at least 10% in the baseline score at 3 and 6 months after the end of the treatment will be considered clinically meaningful. Improvement by 10% of the baseline score at 3 and 6 months will be considered clinically meaningful.

6- Incidence of Treatment-related Adverse Events. Frequency of adverse events of grades 2 or more by Common Adverse Event Toxicity Criteria (CTCAE) version 5.0.

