## **Methodology**

### **Study design**

This is a single-arm, unicentric, single-stage, phase 2 clinical study of therapeutic metaiodobenzylguanidine (MIBG) for patients with metastatic well-differentiated neuroendocrine tumors and radiological progression or intolerance after standard lines of treatment and with MIBG-I positive scan.

Eligible patients will receive MIBG-I in up to 4 doses of 7,400Mbq (200 mCi) each, with an interval of at least 60 days. The administration of the cycles will depend on the results of the haematological exams, therefore, each patient will be able to receive from 1 to 4 cycles; In the experience of A.C.Camargo Cancer Center, most patients receive between 3 and 4 cycles. MIBG-I is administered intravenously to an inpatient, being discharged when reaching limits of radiological exposure recommended by the National Nuclear Energy Commission (invariably, 24 hours). The dose of 200mCi

per application for up to 4 doses of MIBG-I used in this protocol is the same used in routine at the institution and is also used in other PPRT treatments. This dose is safe and practiced by the service for at least a decade.

Clinical and toxicity assessments will take place every 2 weeks with medical history, physical examination and general laboratory until resolution of toxicities (usually 30 days after treatment). Imaging exams (chest, abdomen and pelvis CT scans) and 5-HIAA dosage in 24-hour urine (functioning tumors) will be performed at the beginning of treatment, and every 3 months until progression or exit from the study. Symptom assessment will be conducted using quality of life questionnaires that will be administered before treatment and every 3 months until progression. Toxicities will be measured in all medical visits through CTCAE version 5.0. Consultations, laboratory and imaging tests are already part of the treatment routine of these patients. The extra routine interventions, that is, the study, are the MIBG-I scintigraphy exam, the treatment with MIBG-I and the quality-of-life assessments.

Clinical data will be prospectively collected in an electronic database (REDCap) and will include sex, age, primary tumor site, performance scale status, functionality, metastatic disease duration, metastasis sites, degree of liver impairment, comorbidities, previous treatments, scores of quality of life results and toxicity.

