MIBG-I is administered at a dose of 200mCi intravenously every 8 weeks for up to 4 cycles. Laboratory tests are performed every 15 days, with a focus on assessing myelotoxicity. Laboratory blood tests within the appropriate results (see “inclusion criteria”) allow the administration of the next cycle. In the case of any toxicity with a degree equal to or greater than 3 or intolerable and persistent grade 2 toxicity, the next course of treatment will not be administered until the toxicity is grade 1 or resolves. If the toxicity does not resolve or becomes grade 1 within 8 weeks, the next cycle is not administered, and treatment is stopped.

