### **Potential for cost-effectiveness**

Treatment with MIBG-I, in addition to being available at SUS for the treatment of patients with PggF, appears to offer significant disease control for patients with NET. If the study is positive, it can be cost-effective, as we estimate that 67% of patients will obtain disease control lasting at least 12 months, which will provide time free of toxic therapies, with a low level of evidence and costly to patients and paying sources. In addition, in the absence of a clinical study, these toxic and ineffective therapies are used sequentially, so that each patient will do, in the period of 12 months, at least two of them.

**Table 1.** Treatments used in midgut NET or refractory lung, respective toxicities, efficacy and levels of scientific evidence

Treatment	Disease control rate (%)	Time of disease control (months)	Common toxicities	Evidence level
Folfox/Capox	0-10%	4 – 6	Peripheric neuropathy, diarrhea, nausea, vomiting, thrombocytopenia, anaemia	Retrospective, heterogeneous population*
Capecitabine/ Temozolomide	0-10%	4 – 6	Nausea/Vomiting, diarrhea	Retrospective, phase 1/2 with heterogeneous population
Interferon alpha (3 to 6 million units/week)	20 – 30% (symptoms), 50% (radiological)	10	Psychiatric disorders, immunes, fatigue, myopathy, myelosuppression	Phase III for radiological control, retrospective studies for symptomatic control
Debulking hepatic surgery (R2)	50 – 90% (only symptoms)	19 – 45	Surgical risk compared to a hepatectomy	Retrospective, heterogeneous population
MIBG- 	63 – 80%	12 – 24	Myelosuppression	Retrospective, heterogeneous population

\* neuroendocrine tumors of different origin, efficacy measured with distinct criteria

**TABLE 2.** Complete procedural summary of the study after signing the informed consent form

Procedure	Screening *	Baseline evaluation	D1 **	S2 **	S4 **	...	S8 **	S12 **	S16 **	...	S24 **	Every 12 or 8 weeks
Eligibility assessment												
MIBG scan	X											
Demographics, medical history and previous treatment	X											
Therapeutic MIBG												
200mCi MIBG-  I IV administration			X				X		X		X	
Clinical safety assessment												
Physical exam		X	X	X	X	X	X	X	X	X	X	X
Vital signs, body weight and ECOG		X	X	X	X	X	X	X	X	X	X	X
Signs and symptoms assessment		X	X	X	X	X	X	X	X	X	X	X
Adverse Event Assessment		X		X	X	X	X	X	X	X	X	X

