Laboratory safety assessment												
Hemogram	X	X	X	X	X	X	X	X	X	X	X	
Urea/creatinine	X	X	X	X	X	X	X	X	X	X	X	
Bilirubin, AST/ALT	X	X	X	X	X	X	X	X	X	X	X	
NA, K	X	X	X	X	X	X	X	X	X	X	X	
Pregnancy test in women of childbearing age		X										
Image assessment												
CT of lung, abdomen and pelvis ***	X							X			X	X
Tumor marker **												
Specific hormone		X						X			X	X
Quality of life **												
EORTC QLQ-C30		X						X			X	X
EORTC QLQ-GINET21		X						X			X	X

IV, intravenous; MIBG, metaiodobenzylguanidine

\* within 6 weeks of the first dose and within 4 working days of D1;

\*\* window of +/- 3 days

\*\*\* baseline tests within 8 weeks of D1; Resonance of the abdomen and pelvis in special cases (allergy to iodinated contrast); window +/- 5 days

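### Biochemical response (secondary outcome 4) has no defined window and no confirmation, so the number of readings that can qualify depends on cycles received and on how the wording is read

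*Combined protocol and SAP*

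**What the plan says.** Outcomes, Secondary, item 4 is "Defined by at least 30 percent drop in the tumor marker", the marker being "24-hour urine 5-hydroxyindoleacetic acid (5-HIAA) and/or specific hormone". The timing is "if functioning syndrome, at any time of treatment in relation to pre-treatment value". No visit is named, treatment is given no end, and no second value is required. Nothing says how to count a patient without a qualifying reading. The Statistical plan's non-responder rule covers quality of life only, although efficacy is assessed in everyone who receives at least one dose.

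On sampling, Study design says that imaging and 5-HIAA "will be performed at the beginning of treatment, and every 3 months until progression or exit from the study". In Table 2 the row "Specific hormone" is marked at baseline, S12, S24 and a final column headed "Every 12 or 8 weeks". The fortnightly laboratory list under Security Assessments does not include the marker. The baseline value may be up to 8 weeks old, and no replicate is required.

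On dosing, treatment is given "intravenously every 8 weeks for up to 4 cycles" and Table 2 places doses at D1, S8, S16 and S24. Study design sets a minimum interval of 60 days, says "each patient will be able to receive from 1 to 4 cycles", and expects most patients to have 3 or 4.

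**The concern.** The outcome is a proportion, so each patient needs a comparable opportunity to qualify. Here that opportunity is set by two things the definition leaves open: when treatment ends, and how many 12-weekly readings fall before that end.

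Under a short window, a patient who stops early for toxicity may have no reading at all, and the rate partly measures the number of cycles received. Under a long window, one low value among several is enough, and patients followed longer have more chances to produce one by ordinary variation. The first pushes the rate down and the second pushes it up. In a single-arm trial no comparator would reveal either. A window chosen after the data are seen could also change the reported rate.

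**Working it through.** The plan states no figure for this outcome, so there is none to reproduce. Two checks apply.

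**1. Readings available per patient**

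Inputs: doses at weeks 0, 8, 16 and 24 (Table 2), or at 60-day (8.57-week) spacing (Study design); post-baseline markers at weeks 12, 24, 36 and 48, taking the last Table 2 column as 12-weekly. The last dose for *c* cycles is at week 8(*c* − 1), or 8.57(*c* − 1) at 60-day spacing. A reading counts if its week is no later than the last dose plus the extension in the table.

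| Window | 1 cycle | 2 cycles | 3 cycles | 4 cycles |
|---|---|---|---|---|
| First to last dose | 0 | 0 | 1 (wk 12) | 2 (wk 12, 24) |
| To 8 weeks after last dose | 0 | 1 | 2 | 2 |
| To about 6 months (26 weeks) after last dose | 2 | 2 | 3 | 4 |

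Both spacings give the same counts (60-day last doses: weeks 0, 8.6, 17.1 and 25.7). The zero for 2 cycles assumes dose 2 is on time. A toxicity delay of up to 8 weeks is allowed, so dose 2 could fall as late as week 8 + 8 = 16, after the week-12 reading, and that patient would then have one reading. The third row assumes no progression or exit before the last reading counted.

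**2. False response when the marker has not changed**

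Assumptions: independent log-normal within-patient variation, one baseline value, one marker. The within-patient CV is not in the documents and is varied. With σ = √ln(1 + CV²), one reading qualifies falsely with probability Φ(ln 0.70 / (σ√2)). At CV 20%, σ = 0.198, so Φ(−0.357/0.280) = Φ(−1.27) = 10%. For the lowest of several readings against the same baseline, 400,000 patients were simulated:

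| CV | 1 reading | Lowest of 2 | Lowest of 4 | Two consecutive, 2 readings | Two consecutive, 4 readings |
|---|---|---|---|---|---|
| 10% | 0.6% | 1.1% | 2.0% | 0.1% | 0.1% |
| 20% | 10% | 17% | 26% | 3.3% | 6.7% |
| 30% | 20% | 31% | 44% | 8.5% | 16% |

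The wording also allows either 5-HIAA or a specific hormone to qualify. A patient with both would have further chances, which are not modelled.

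**What confirmation does and does not do.** At CV 20%, confirmation cuts the absolute error, but the ratio of four readings to two rises from 26/17 = 1.5 to 6.7/3.3 = 2.0. Confirmation alone therefore leaves the rate dependent on cycle count. A single fixed visit gives every patient one reading and removes that dependence.

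**The case against.** The best defence is that nobody would read treatment as the interval between first and last injection. For a one-dose patient that would be a single day, in a protocol that expressly allows one cycle. Markers continue until progression or exit, so anyone still on study has a week-12 value, and the natural meaning is best post-baseline value. Unconfirmed best response is a legitimate descriptive choice, and at a CV of 10% the noise is negligible.

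Much of this stands. A reader might infer that the plan makes early stoppers automatic non-responders, or that everyone with 1 or 2 cycles lacks a reading during dosing. The documents support neither: no such rule is written, the result needs the narrow window, and for 2 cycles it also needs undelayed dosing. Since most patients are expected to have 3 or 4 cycles, a minority would be affected. Four readings likewise require four cycles and no progression or exit to week 48.

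What does not fall is the core. The natural reading is not the one written, and adopting it brings in the lowest-of-several problem with a count that varies by patient. Marker stability is already part of disease control at 3 and 6 months for functioning tumors, but that does not define this separate 30% outcome.

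**Conclusion.** The point holds as a minor one. As written, the outcome either leaves some early stoppers with no chance to respond (0, 0, 1 and 2 readings for 1 to 4 cycles) or credits the lowest of 2, 2, 3 and 4 unconfirmed values. The counts follow from the planned schedule. The direction of the noise effect is certain under the stated model, but its size rests on an assumed CV: one reading versus the lowest of four differs by about 1 percentage point at CV 10%, 16 at 20% and 24 at 30%.

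A reader might go further and infer that the trial's main conclusion is affected. It is not. This outcome is secondary, descriptive and confined to functioning tumors; the sample size of 22 was derived for disease control, and the primary definition does not use the 30% rule.

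**What to change.** Amend item 4 and the Statistical plan as follows.

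- Name the qualifying marker for each functioning patient at baseline.
- Make the reported rate the proportion with a drop of at least 30% at the 3-month and, separately, the 6-month post-treatment assessment, the time points already used for disease control and quality of life. Count treated functioning patients with no evaluable reading as non-responders.
- Alongside it, report best response from first dose to the 6-month assessment, confirmed at the next scheduled reading, with the unconfirmed best drop as description. State whether a drop first seen at 6 months may be confirmed later.
- Settle whether the last Table 2 column means 12 or 8 weeks for markers.
- Define the end of treatment and how scheduled readings map to the fixed visits. Taking it as the last dose, and 3 and 6 months as 12 and 24 weeks, the visits fall at weeks 12 and 24 for 1 cycle, 20 and 32 for 2, 28 and 40 for 3, and 36 and 48 for 4. The 12-weekly readings coincide for 1 and 4 cycles; for 2 and 3 cycles the nearest is 4 weeks away.

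The cost is wording, because the readings are already scheduled until progression or exit. The headline rate will be somewhat lower, and patients who progress before the fixed visit or the confirming reading will not count as responders.

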## **Methodology**

### **Study design**

This is a single-arm, unicentric, single-stage, phase 2 clinical study of therapeutic metaiodobenzylguanidine (MIBG) for patients with metastatic well-differentiated neuroendocrine tumors and radiological progression or intolerance after standard lines of treatment and with MIBG-I positive scan.

Eligible patients will receive MIBG-I in up to 4 doses of 7,400Mbq (200 mCi) each, with an interval of at least 60 days. The administration of the cycles will depend on the results of the haematological exams, therefore, each patient will be able to receive from 1 to 4 cycles; In the experience of A.C.Camargo Cancer Center, most patients receive between 3 and 4 cycles. MIBG-I is administered intravenously to an inpatient, being discharged when reaching limits of radiological exposure recommended by the National Nuclear Energy Commission (invariably, 24 hours). The dose of 200mCi

per application for up to 4 doses of MIBG-I used in this protocol is the same used in routine at the institution and is also used in other PPRT treatments. This dose is safe and practiced by the service for at least a decade.

Clinical and toxicity assessments will take place every 2 weeks with medical history, physical examination and general laboratory until resolution of toxicities (usually 30 days after treatment). Imaging exams (chest, abdomen and pelvis CT scans) and 5-HIAA dosage in 24-hour urine (functioning tumors) will be performed at the beginning of treatment, and every 3 months until progression or exit from the study. Symptom assessment will be conducted using quality of life questionnaires that will be administered before treatment and every 3 months until progression. Toxicities will be measured in all medical visits through CTCAE version 5.0. Consultations, laboratory and imaging tests are already part of the treatment routine of these patients. The extra routine interventions, that is, the study, are the MIBG-I scintigraphy exam, the treatment with MIBG-I and the quality-of-life assessments.

Clinical data will be prospectively collected in an electronic database (REDCap) and will include sex, age, primary tumor site, performance scale status, functionality, metastatic disease duration, metastasis sites, degree of liver impairment, comorbidities, previous treatments, scores of quality of life results and toxicity.

### **Study population**

Research participants will be recruited from the Clinical Oncology outpatient clinics and must meet all the inclusion criteria and none for exclusion.

#### **Inclusion criteria**

- Age greater than or equal to 18 years.
- Well-differentiated metastatic NET from GEP, unknown primary with hepatic metastases or advanced/metastatic lung, inoperable, with no possibility of curative treatment.
- MIBG-I scintigraphy with positive expression in at least one lesion that presents significant uptake and compatible with therapeutic effectiveness.

- Disease with radiological progression (at least 10% tumor volume growth) in the last 12 months or with clinical and biochemical progression to functional NET according to clinical judgment.
- Progression or intolerance to previous standard treatments according to scenario (private [somatostatin analogue, everolimus] or public [somatostatin analogue]).
- Measurable disease.
- ECOG performance scale 0 to 2.
- Adequate organic function as defined by the following criteria:
  - Aspartate serum aminotransferase (AST), alanine serum aminotransferase (ALT)  $\leq$  2.5 times the upper limit of normal of the local laboratory (ULN-LL);
  - Total serum bilirubin  $\leq$  2.0 x ULN-LL;
  - Absolute neutrophil count  $\geq$  1,500/mm^3;
  - Platelet count  $\geq$  100,000/mm^3;
  - Hemoglobin  $\geq$  9.0 g/dL;
  - Estimated creatinine clearance using the MDRD equation  $\geq$  60ml/min
  - Informed consent form signed by the patient or legal representative.

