Adult patients, ECOG 0-2, with good organic functions, with progressing metastatic or locally advanced NET of GI or lung origin, with refractory disease or intolerant to available standard therapies, and with positive MIBG-I scintigraphy in metastatic lesions are eligible for receive up to 4 doses of 7,400Mbq (200 mCi) each, with an interval of at least 60 days. The primary outcome will be the disease control rate (DCR) at 6 months after the end of treatment, per RECIST 1.1; secondary outcomes will be DCR at 3 months post treatment, progression-free survival, radiological and biochemical response (functional NET), toxicities and quality of life measured by the EORTC QLQ-C30 and GINET21 questionnaires. Laboratory tests and clinical evaluation will be performed every 2 weeks during the study; Imaging exams will be performed every 3 months until progression. The study sample will be 22 patients. For this calculation, we consider the H0 of DCR in 6 months of 40% (placebo arm of phase III studies in TNE), H1 as 67%. Two-tailed type I error margin of 10%, power of 80% and loss of follow-up/non-adherence of 10% were considered. We estimated a 50% screening failure (50% positivity on MIBG-I).

If the study is positive, it can be cost-effective, as we estimate that 67% of patients will obtain disease control lasting at least 12 months, which will provide time free of toxic therapies with a low level of evidence and costly to patients and paying sources. In addition, the study has the potential to change the treatment guidelines for NET, facilitating the incorporation of MIBG-I as a therapeutic strategy in the treatment protocols for NET at A.C.Camargo Cancer Center. The study, therefore, may allow the institution in the future to offer treatment with MIBG-I to patients with supplementary health, recovering the costs invested in the MIBNET study.

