## **Introduction**

Neuroendocrine tumors (NET) are rare neoplasms, but with increasing incidence and prevalence in the last decades. In more than half of the cases, they present metastatic and incurable at diagnosis. Few effective therapies are approved for these tumors (somatostatin analogues, everolimus, and sunitinib), none have demonstrated gains in overall survival, and none is approved in the Brazilian public health system (SUS).

Well-differentiated NET express, in more than 80% of the cases, somatostatin receptors. Somatostatin analogues, lanreotide or octreotide, have anti-proliferative and anti-secretory activity, and, frequently, are considered the first-line treatment in the metastatic setting. Somatostatin receptors expression, through scintigraphy scan marked with radionuclide and octreotate (Octreoscan©) or positron emission tomography labelled with Ga (Ga-PET-CT), is mandatory to effectively indicate the treatment with Lutetium^177 radionuclide. The NETTER-1 study demonstrated the efficacy of Lutetium^177, a type of peptide receptor radionuclide therapy (PRRT), in combination with long-acting releasing (LAR) octreotide 30 mg in second-line, with progression-free survival of approximately 40 months versus 8.5 months for the group treated only with LAR octreotide monthly in patients with midgut NET metastatic (HR: 0.20;  $p < 0.0001$ ). The NETTER-1 study established one more therapeutic strategy to NET, the PRRT.

However, invariably, metastatic NET patients develop disease progression to standard treatment. Different chemotherapeutic regimens (FOLFOX, cisplatin/etoposide, cisplatin/irinotecan, capecitabine/oxaliplatin, and capecitabine/temozolomide), hepatic debulking surgery, and interferon alpha are used based on small phase 2 trials and/or retrospectives studies. In the Brazilian consensus of NET, these treatment modalities, even with low evidence level, are recommended when there are no other effective treatments available. Although some patients could benefit from these therapeutic options, the results relating to tumor response and quality of life tend to be modest and the toxicity significant (Table 1). Therefore, new treatment should be investigated in this context.

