#### Exclusion Criteria

- Patients already treated with MIBG-I.
- History of serious clinical or psychiatric illness that, due to clinical judgment, may pose a risk for participation in this study.
- Patients being treated with other protocols with experimental drugs.
- Patients who have had recent major surgery less than 4 weeks ago.
- Patients who received chemotherapy or other cancer therapy less than 3 weeks ago.
- Pregnant or lactating patients.
- Another synchronic neoplasia that requires systemic treatment.

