### **Security Assessments**

#### **Baseline Assessments:**

After signing the informed consent form, patients will be submitted to the baseline eligibility assessment (see Table 2).

Within 6 weeks of the first treatment dose: search for noraepinephrine expression by MIBG-I scintigraphy. If positive, eligibility is confirmed, and the following procedures are:

- Within 4 days of D1C1: Medical history, including previous diagnosis and treatment, history of other diseases (active and resolved), medications in use and general demographic data. Complete physical examination, ECOG performance index (PS) and vital signs.
- Within 4 days of the first treatment dose, laboratory tests will be performed: blood count, urea, creatinine, ALT, AST, total bilirubin, sodium, potassium, and pregnancy test for women of childbearing age; these patients will be oriented to contraception.
- Baseline imaging exams performed within 8 weeks of the first treatment dose will be accepted: CT scan (or MRI, if applicable) of the abdomen, pelvis and chest.
- For patients with functioning NET, it will be accepted that baseline tumor marker exams have been performed within 8 weeks of the first treatment dose (eg 5HIAA in 24-hour urine).

With the exception of MIBG scintigraphy, which is used routinely for patients with PggF (but not TNE), all of the above tests are already part of the routine in the treatment of NET at A.C.Camargo Cancer Center.

*Safety assessments during treatment:*

Patients will be evaluated clinically and with laboratory tests (Table 2) every 15 days between treatment cycles and after completion until resolution of any adverse treatment effects. +/- 3 days window will be allowed.

- Complete physical examination, measurement of vital signs, weight measurement, ECOG, use of medications.
- Assessment of adverse events.
- Laboratory evaluation: blood count, urea, creatinine, ALT, AST, total bilirubin, sodium, potassium, and others, if clinically indicated.

To grade toxicities we will use the CTCAE 5.0 criteria. Patients who have intolerable grade 2 or grade 3 toxicity that the investigator deems to be related to MIBG-1131 will have their treatment cycle delayed to grade 1 or resolution. If there is no reduction in the intensity of the adverse event to grade 1 within 8 weeks, treatment is discontinued.

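### Entry progression is not tied to the most recent antitumour therapy, so some patients can enrol while still controlled by it, and that residual control can count towards the single-arm disease control rate

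*Combined protocol and SAP*

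**What the plan says.** Two separate bullets under Inclusion criteria govern entry.

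- **Progression.** The patient needs "Disease with radiological progression (at least 10% tumor volume growth) in the last 12 months". A second, alternative route is worded as follows: "or with clinical and biochemical progression to functional NET according to clinical judgment". That route carries no clear time window.
- **Prior therapy.** The patient needs "Progression or intolerance to previous standard treatments according to scenario (private [somatostatin analogue, everolimus] or public [somatostatin analogue".

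Neither bullet refers to the most recent therapy. Exclusion Criteria rules out "Patients who received chemotherapy or other cancer therapy less than 3 weeks ago", with a separate 4-week limit after major surgery. Under Baseline Assessments, "Baseline imaging exams performed within 8 weeks of the first treatment dose will be accepted", so the baseline scan may have been taken while the previous therapy was still being given.

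The Abstract describes patients "with progressing metastatic or locally advanced NET of GI or lung origin" and also admits those who are intolerant. The Study design section likewise accepts either radiological progression or intolerance after standard lines.

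The primary outcome is freedom from RECIST 1.1 progression six months after treatment ends, so stable disease counts as control. Patients with a functioning syndrome must also gain 10% on the GINET21 score and have stable or falling markers. The comparison is a single arm against 40%, taken from placebo arms of phase III trials.

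**The concern.** Two patients show the gap.

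1. A private-sector patient progressed on a somatostatin analogue 11 months ago, was stable on everolimus for 9 months, and stopped it for intolerance 3 weeks ago. The old progression meets the first bullet and intolerance meets the second.
2. A public-sector patient progressed on a somatostatin analogue 10 months ago, then had Lutetium-177 and is now stable. Only the analogue is on the public list, so the response to the later therapy is never checked.

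Neither patient is shown to be progressing at entry. If the earlier treatment is still holding the disease, a non-functioning patient of this kind may be counted as controlled even if MIBG adds nothing. There is no control arm to reveal this. Previous treatments are recorded, but no analysis by last therapy or time since it is planned. The disease control rate and progression-free survival could both look better than the drug deserves.

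**Working it through.** **1. The plan's own figure.** Inputs from the Statistical plan: null 40%, alternative 67%, two-sided error 10% (5% per tail), power 80%, loss 10%.

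n = [(1.645·√(0.40·0.60) + 0.842·√(0.67·0.33)) / 0.27]² = [(0.806 + 0.396) / 0.27]² = 19.8, rounded up to 20; 20 × 1.1 = 22. The stated sample size reproduces.

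**2. The success cut-off.** The plan states none. Exact binomial tails for n = 22:

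| Success at | Error at 40% | Power at 67% |
|---|---|---|
| 13 or more | 5.5% | 84.5% |
| 14 or more | 2.1% | 71.9% |

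Only 14 or more respects 5% per tail, so it is the main case here.

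**3. When the endpoint falls.** With cycles 8 weeks apart, the assessment comes 26 weeks after the first dose for one cycle, 16 + 26 = 42 weeks for three and 24 + 26 = 50 weeks for four. The Study design section says most patients receive 3 to 4 cycles.

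**4. How much control could remain without MIBG.** Assumptions: exponential time to progression, the clock restarted at the first dose, and the documents' durations read as medians m. The share still controlled at t months is 0.5^(t/m).

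| Prior therapy (source) | m, months | 26 weeks | 42 weeks | 50 weeks |
|---|---|---|---|---|
| Lutetium-177 plus octreotide (Introduction) | 40 | 0.90 | 0.84 | 0.82 |
| Interferon (Table 1) | 10 | 0.66 | 0.51 | 0.45 |
| Chemotherapy, upper figure (Table 1) | 6 | 0.50 | 0.33 | 0.26 |

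The first row rests on the Introduction's "with progression-free survival of approximately 40 months versus 8.5 months". At 42 to 50 weeks Lutetium-177 is far above the 40% null, interferon slightly above it, and chemotherapy below it. The documents give no duration of control after everolimus is stopped. The debulking range in Table 1 (19 to 45 months) covers symptoms only and is not used.

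**5. Effect on the error rate.** Let f be the share of entrants controlled by an earlier therapy and c their control rate with no MIBG effect. The documents give neither. The rate with an inactive drug is p = (1 − f)·0.40 + f·c, and the false-positive risk is the binomial tail at p. For c = 70%:

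| f | p | 14 or more of 22 | 13 or more of 22 |
|---|---|---|---|
| 0 | 40% | 2.1% | 5.5% |
| 10% | 43% | 4.2% | 9.6% |
| 25% | 47.5% | 9.6% | 19.1% |
| 40% | 52% | 19.0% | 32.7% |

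At f = 25% and 14 or more, c = 50%, 60% and 80% give p = 42.5%, 45% and 50%, and risks of about 3.7%, 6.2% and 14.3%.

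**The case against.** The strongest reply has five parts.

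- **Intent is stated.** The Abstract says progressing, and the rationale speaks of refractory disease. These phrases show the aim but set no timing, and the Abstract and Study design also admit intolerance. The operative criteria leave the gap open.
- **The endpoint is stricter for some patients.** Functioning patients need a 10% quality-of-life gain and stable or falling markers, which residual control alone may not deliver. The Introduction says MIBG uptake is seen especially in G1 and functioning tumours, so this could cover a fair part of the sample. It stands, and it dampens the effect.
- **Carry-over fades.** Among therapies with a radiological figure, only Lutetium-177 reaches 70% at the usual assessment time, and its 40 months belongs to a regimen that includes octreotide. This stands. A reader might infer that any recent therapy inflates the result; the documents' durations do not support that.
- **The null may already contain such patients.** The entry rules of the placebo trials are not in the documents, so the direction of bias against 40% is possible but not proven. This stands.
- **Tightening entry has a price.** Requiring progression after the last therapy would make patients who stopped a drug for intolerance while stable wait, narrowing a route that the plan admits deliberately. This stands against treating that requirement as the only remedy.

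**Conclusion.** The gap in the criteria is real. Patients controlled by an intervening therapy can enrol through the intolerance branch or through therapies outside the listed drugs, and their residual control can raise the disease control rate and progression-free survival. The effect is plausible mainly after Lutetium-177, modest after interferon, and absent or reversed after chemotherapy when 3 to 4 cycles are given.

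Its size cannot be derived from the documents. At an assumed 70% control rate and the cut-off that respects 5% per tail, error stays below 5% if a tenth of entrants are affected and reaches 9.6% at a quarter and 19.0% at two fifths. A reader might take the 19.1% and 32.7% seen at 13 or more as the headline, but that cut-off already exceeds the planned error before any carry-over. Nor do the documents show that a positive result would be due to carry-over: the share affected is unknown, and the illustration applies one rate to functioning and non-functioning patients alike.

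**What to change.** 1. For every patient, including those already enrolled, record the date of the qualifying progression and the type and end date of the last antitumour therapy (systemic, radionuclide, liver-directed or surgical).
2. Pre-specify the disease control rate, with exact interval, and progression-free survival both with and without patients whose progression predates that therapy. State that efficacy will not be claimed if the result depends on them. Define dependence beforehand and on the estimate, since the reduced set is smaller and could lose significance through size alone.
3. Reconcile the progression bullet with the Abstract's description and with the intolerance route in the Abstract, Study design and Inclusion criteria. State whether progression must fall on or after the last therapy, for the radiological and the clinical/biochemical routes alike.

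Items 1 and 2 cost a few data fields and one planned analysis. Previous treatments are already on the data list, but progression dates and earlier scans are not. If item 3 tightens entry, recruitment slows somewhat. At 35 to 40 patients a year over two years, and the 40% or 50% MIBG positivity that the two sections give, there are about 70 × 0.40 = 28 to 80 × 0.50 = 40 positive patients for 22 places before other criteria apply. Sample size and treatment do not change.
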